6.1 Endpoints

6.1.1 Primary Safety Endpoint (IDE and CAP)

The primary safety endpoint is the rate of major complications through 180 days after an attempted ADO II AS device implant (refer to Appendix B for definition).

6.1.1.1 Analysis Methodology

The proportion of subjects experiencing a primary safety endpoint through 180 days will be estimated. The 95% confidence interval for the proportion of subjects experiencing a primary safety endpoint will be calculated using the exact binomial method. [REDACTED]

[REDACTED]

[REDACTED]

6.1.2 Primary Effectiveness Endpoint (IDE and CAP)

The primary effectiveness endpoint is the rate of effective closure of the ductus arteriosus among subjects with a successful ADO II AS implant as assessed by the presence of either a Grade 0 or Grade 1 shunt (see Section 4.4.1) at the six-month follow-up by transthoracic echocardiography.

6.1.2.1 Analysis Methodology

The proportions of subjects who have effective closure of the ductus arteriosus at the 6-month follow-up will be estimated. The 95% confidence interval for the rate of effective closure of the ductus arteriosus will be calculated using the exact binomial method. [REDACTED]

[REDACTED]

[REDACTED]

[REDACTED]

[REDACTED]

6.1.3 Secondary Endpoint (IDE and CAP)

The secondary endpoint is the rate of significant obstruction of the pulmonary artery or aorta through the 6-month follow-up visit per the following definitions:

1. Significant obstruction of the left pulmonary artery is defined as less than 30% flow to the left lung by lung perfusion scan or a peak instantaneous gradient in left pulmonary artery ≥ 35 mmHg by echocardiogram if lung perfusion scan is not available. OR
2. Significant obstruction of the aorta is defined as a gradient of ≥ 20 mmHg in the aortic isthmus by invasive aortic catheterization or a mean gradient ≥ 20 mmHg in the aortic isthmus by echocardiogram if invasive aortic catheterization is not available.

6.1.3.1 Analysis Methodology

The proportions of subjects experiencing a secondary endpoint through the 6-month follow-up visit will be estimated. The 95% confidence interval for the proportion of subjects experiencing a secondary endpoint will be calculated using the exact binomial method. [REDACTED]

[REDACTED]

[REDACTED]

[REDACTED]

6.1.4 Descriptive Endpoints and Additional Data for Pivotal IDE Subjects

The following endpoints will be summarized using descriptive statistics.

- **Implant success:**
The frequency and percentage of implant success (defined in Section 6.1.3.2) will be reported. This analysis will include enrolled subjects.
- **PDA shunt status at each follow-up visit:**
The frequency and percentage of PDA shunt status at each follow-up visit, as assessed by the Echo Core Lab, will be reported. Shunt sizes categories are: Grade 0/1, 2, and Grade 3/4. This analysis will include subjects who achieve a successful implant.
- **Obstruction measurements at each follow-up visit:**
The frequency and percentage of significant obstruction of the left pulmonary artery and the frequency and percentage of significant aortic obstruction (defined in Section 6.1.3) at each follow-up visit will be reported. Both analyses will include subjects who achieve a successful implant.
- **Major and Minor Complications:**
The frequency and percentage of major and minor complications (refer to Appendix B for definition) from the time of the implant procedure will be reported.
- **Death:**
The frequency and percentage of death will be reported.

[REDACTED]

- Additional data:
Demographics and baseline characteristics, procedure information, left ventricular function and dimensions, pulmonic and tricuspid regurgitation, adverse events, withdrawal and protocol deviations will also be summarized.

6.1.5 Descriptive Endpoints and Additional Data for CAP Subjects

The following endpoints will be summarized using descriptive statistics.

- Implant success:
The frequency and percentage of implant success (defined in Section 6.1.3.2) will be reported. This analysis will include enrolled subjects.
- Major and Minor Complications:
The frequency and percentage of major and minor complications (refer to Appendix B for definition) from the time of the implant procedure will be reported.
- Death:
The frequency and percentage of death will be reported.
- Additional data:
Demographics and baseline characteristics, procedure information, left ventricular function and dimensions and pulmonic and tricuspid regurgitation at 6 months, and adverse events, withdrawal and protocol deviations will also be summarized at each follow-up visit.

[REDACTED]

[REDACTED]

[REDACTED]

[REDACTED]

[REDACTED]

[REDACTED]

[REDACTED]

[REDACTED]

[REDACTED]

[REDACTED]

[REDACTED]

6.7 Deviations from Statistical Plan

If any deviations from the original statistical plan occur, such deviations will be documented in the clinical study report or statistical report containing the analysis results.

7 Risks and Benefits

Risks associated with the device are managed in accordance with ISO 14971. The risk analysis included an objective review of published and available unpublished medical and scientific data. The sections below provide an overview of residual risks identified in the risk management report and anticipated benefits of the medical device. The additional tests and assessments required by the clinical investigation were analyzed for additional risks to subjects of this clinical investigation, and are incorporated in the sections below.

7.1 Risks associated with the Device under Investigation

7.1.1 Anticipated Adverse Device Effects

The risks associated with the implant procedure are similar to those of other cardiac catheterization procedures in infants and children and are documented below. Radiation risks associated with the procedure are comparable to a diagnostic catheterization procedure.

- Air embolism
- Allergic reaction
- Arrhythmia
- Arteriovenous fistulae
- Bleeding at the access site
- Brachial plexus injury
- Bruising
- Cardiac tamponade
- Death
- Deep venous thrombosis
- Dissection
- Embolism
- Endocarditis
- Hematoma
- Hemodynamic compromise
- Infection
- Myocardial infarction
- Perforation
- Peripheral pulse loss
- Pseudoaneurysm
- Respiratory distress
- Stroke/transient ischemic attack
- Thrombosis
- Valve damage
- Vascular access site injury
- Vascular occlusion
- Vessel damage

[REDACTED]

The following is a list of the anticipated adverse device effects associated with the ADO II AS device under investigation:

- Air embolism
- Allergic dye reaction
- Allergic drug reaction
- Anesthesia reactions
- Apnea
- Arrhythmia
- Bacterial endocarditis
- Bleeding
- Cardiac perforation
- Cardiac tamponade
- Chest pain
- Device embolization
- Device erosion
- Death
- Fever
- Hemolysis
- Headache/migraine
- Hypertension
- Hypotension
- Myocardial infarction
- Nickel sensitization
- Nickel toxicity
- Palpitations
- Partial obstruction of the Aorta
- Partial obstruction of the Pulmonary Artery
- Pericardial effusion
- Pericarditis
- Peripheral embolism
- Pleural effusion
- Pulmonary embolism
- Reintervention for device removal
- Stroke
- Transient ischemic attack
- Thrombus
- Valvular regurgitation
- Vascular access site injury
- Vessel perforation
- Carcinogenicity

Potential carcinogenicity risk. The ADO II AS device consists of a nickel-titanium alloy. In vitro testing has demonstrated that that nickel is released from this device for a minimum of 60 days. Some forms of nickel have also been associated with carcinogenicity (ability to cause cancer) in animal models. In humans, carcinogenicity has been demonstrated only through an inhalation route (breathing nickel in), which will not occur with this procedure.

7.1.1 Risks associated with Clinical Investigation Assessments

The risks associated with the ADO II AS device implant procedure are similar to those of other cardiac catheterization procedures. Radiation risks associated with the procedure are comparable to a diagnostic catheterization procedure.

The risks associated with the ADO II AS device are similar to other implantable cardiac occlusion devices.

Additional study required procedures are listed below with the associated risks/discomforts.

Blood Draw

There may be some minor discomfort and/or anxiety associated with drawing blood including pain or bruising associated with the needle from the blood draw. Fainting and local infection can also occur.

Aortic Catheterization

Aortic catheterizations have a risk for injury to the vessel, allergic reaction to dye, anesthesia reaction irregular heartbeat, infection, poisonous products in the bloodstream, loss of blood flow to the extremities from the catheter placement, damage or injury to the heart, lungs, valves or vessels from the catheter or wire advancement, air or blood clot formation in a vessel or heart which may cause temporary or complete blockage of blood flow to the heart, brain, or extremities, irregular blood pressure, fever, injury to the nerves that control the arm or shoulder, kidney dysfunction due to exposure to contrast media (liquid used for imaging) and death.

Lung Perfusion Scan

Lung perfusion scans expose the patient to a small dose of radiation (about as much radiation as natural exposure over a year). There is always a slight risk from being exposed to radiation.

Computed Tomography (CT) Aortic Angiography

There may be risks due to the radiation used during the CT imaging. There is also a risk for an allergic response to the contrast media/dye used during the CT imaging procedure.

Magnetic Resonance (MR) Aortic Angiography

MR imaging use magnetic and radio waves to generate images of the vasculature. The risk from these waves is no greater than experienced in daily life. There is also a risk for an allergic response to the contrast media/dye used during the MRI procedure.

Echocardiogram

The electrodes placed on subject's chest may cause discomfort such as redness or itching. The subject may feel slight pressure from the transducer or probe that the technician utilizes to take measurements.

Chest X-ray

The risks of chest x-rays include exposure to small doses of radiation (about as much radiation as natural exposure over 10 days). There is always a slight risk from being exposed to any radiation.

Electrocardiogram

The electrodes placed on subject's chest can sometimes cause discomfort such as redness or itching.

7.2 Possible interactions with concomitant treatments

The risks from intra-procedural medications administration upon undergoing ADO II AS implant are no different from the risks associated with medications prescribed during a cardiac catheterization procedure or implant of commercially available transcatheter PDA occluder device.

7.3 Risk Control Measures

Every possible effort will be taken to minimize the risks, including:

- Careful selection of experienced Investigators for the clinical investigation
 - Cardiologists with training and education in pediatric cardiology and experience using transcatheter techniques to close PDAs
 - Prior experience with transcatheter closure procedures using devices such as ADO, ADO II or other similar devices with a minimum of 60 cases
 - Institutions will have the necessary infrastructure to support trial procedures:
 - Cardiac catheterization lab or NICU bedside capability to perform intra-procedural echocardiography and fluoroscopy
 - Anesthesiology support, as needed
 - Catheterization laboratory, operating room, post anesthesia recovery, intensive care and step down unit spaces to accommodate cases with and without complications
 - On-site emergency cardiac surgery services
- Adequate monitoring for each clinical investigation site
- Conducting the clinical investigation in accordance with the CIP, all applicable laws and regulations and any conditions of approval imposed by the appropriate IRB or applicable regulatory authorities where the clinical investigation is performed
- Preparation of the ADO II AS device and implant procedure in accordance with the device IFUs
- Training of Investigators both on the CIP and ADO II AS implant procedure
 - All site staff will participate and complete a training module on the CIP
 - All implanting physicians must complete an implanter training module
 - Implanting physicians with no prior successful transcatheter PDA closure experience with ADO II AS in small infants (≤ 2 kg) will receive proctoring for a minimum on one case.
- Assessment of continuing safety of subjects in the clinical investigation by an independent CEC

The following measures have also been taken to reduce the risks of specific study device related adverse events:

- Subject eligibility criteria include maximum diameter and minimum lengths of the PDA to be treated with the ADO II AS which should reduce the likelihood of partial obstruction of the pulmonary artery or aorta.
- Whenever possible, subjects will be given a loading dose of Heparin at the beginning of the procedure to reduce the risk of thrombus formation on the devices. The use of heparin in patients with a risk of bleeding is considered optional.
- The physicians will be trained on the procedure, specifically device size selection and placement, to reduce the risk of device embolization, partial obstruction of the aorta or pulmonary artery and hemolysis which could be potentially caused by the ADO II AS.
- The physicians will be instructed to use their clinical judgement to monitor subjects for potential adverse events related to nickel and to report such events with the goal of protecting the welfare of the subject if the root cause of the adverse event is determined to be nickel related, paying special attention to subjects weighing less than 6kg at baseline

- The physicians will be encouraged to utilize an antegrade implant approach, while avoiding the need for arterial access. Additionally, the protocol will not require the acquisition of invasive hemodynamic measurements to minimize complication and shorten procedure time. Device implant is recommended to be performed based on echocardiographic and fluoroscopic guidance without needing to utilize intravenous contrast agents and angiograms.
- Physicians are required to follow The American Heart Association Recommendations for endocarditis prophylaxis during the clinical study.

7.4 Anticipated Benefits

The ADO II AS will be implanted via transcatheter approach, therefore avoiding open heart surgery. The device has been designed to be delivered through a 4F catheter delivery system which may decrease the risk of vascular access site injuries and temporary loss of peripheral pulse compared to a 5F or larger catheter delivery system. The device has also been designed to conform to different defect lengths allowing this device to be placed in short PDAs.

7.5 Risk-to-Benefit Rationale

Risks associated with participating in this clinical study are not anticipated to be any different from risks associated with undergoing implant with commercially available transcatheter devices such as ADO II or coils. The potential benefit of participating in this clinical study is close follow-up of the subject by their treating physicians. Potential benefits of the ADO II AS device compared to currently available options are minimally invasive PDA closure with a smaller device suitable for a smaller sized PDA, and a lower rate of complications. Future neonatal patients with PDA may benefit from the results of this clinical trial.

7.6 History of device modifications or recall

There have been no recalls or field actions during the global marketing and sale of the ADO II AS device.

8 Requirements for Investigator records and reports

8.1 Deviations from CIP

A deviation is defined as an instance(s) of failure to follow, intentionally or unintentionally, the requirements of the CIP. The investigator should not deviate from the CIP.

In some cases, failure to comply with the CIP may be considered failure to protect the rights, safety and well-being of subjects; such non-compliance exposes subjects to unreasonable risks. Examples: failure to adhere to the inclusion/exclusion criteria, failure to perform safety assessments intended to detect adverse events. Investigators should seek to minimize such risks by adhering to the CIP.

The PI must maintain accurate, complete, and current records, including documents showing the date of and reason for each deviation from the CIP. Relevant information for each deviation will be documented as soon as possible on the applicable CRF. The site will submit the CRF to the Sponsor.

The PI is required to adhere to local regulatory requirements for reporting deviations to IRB.

An investigator shall notify the Sponsor and the reviewing IRB of any deviation from the investigational plan to protect the life or physical well-being of a subject in an emergency. Such notice shall be given as soon as possible, but in no event later than 5 working days after the emergency occurred. Except in such an

emergency, prior approval by the Sponsor is required for changes in or deviations from a plan, and if these changes or deviations may affect the scientific soundness of the plan or the rights, safety, or welfare of human subjects, FDA and IRB is also required.

8.2 Adverse Event Reporting

Safety surveillance within this trial (and the safety reporting performed by the investigator), starts as soon as the subject is enrolled. The safety surveillance and the safety reporting will continue until the last investigational visit has been performed, the subject is deceased, the subject/investigator concludes his/her participation into the clinical investigation or the subject withdrawal from the clinical investigation.

All adverse event data required to be reported will be collected throughout the clinical investigation and will be reported to the Sponsor on a CRF.

Adverse events will be monitored until they are adequately resolved or the subject has ended his/her participation in the trial, whichever comes first. The status of the subject's condition should be documented at each visit.

For the purposes of this clinical investigation the following events will be reported (see **Appendix B** for definitions):

- Unanticipated adverse device effects
- All adverse events viewed/interpreted by investigator to be potentially related to either a) the implant procedure or b) the study device (ADO II AS) regardless of seriousness

Note – If relatedness is unknown or cannot be determined, then the event must be reported.

Note – if a procedure is abandoned and a non-study device is used to close the PDA, adverse events associated with the non-study device will not be reported.

Records relating to the subject's subsequent medical course must be maintained and submitted (as applicable) to the Sponsor until the event has subsided or, in case of permanent impairment, until the event stabilizes and the overall clinical outcome has been ascertained. Adverse events will be monitored until they are adequately resolved. The status of the subject's condition should be documented at each visit.

SAE Reporting

Reportable adverse events that are deemed by the investigator to be serious should be reported to the Sponsor as soon as possible but no later than outlined below.

Clinical Site	Reporting timelines
All Sites	SAEs must be reported to the Sponsor no later than 3 calendar days from the day the site personnel became aware of the event or as per the investigative site's local requirements, if the requirement is more stringent than those outlined above.

The date the site staff became aware the event met the criteria of an SAE must be recorded in the source document. The Investigator will further report the SAE to the local IRB/EC according to the institution's IRB/EC reporting requirements.

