5.7 Subject Withdrawal

Subjects must be informed about their right to withdraw from the clinical investigation at any time and for any reason without sanction, penalty or loss of benefits to which the subject is otherwise entitled. Withdrawal from the clinical investigation will not jeopardize their future medical care or relationship with the investigator. Subjects will be requested to specify the reason for the request to withdraw. The investigator must make all reasonable efforts to retain the subject in the clinical investigation until completion of the clinical investigation.

If a subject misses one or more of the scheduled follow-up visits (i.e., does not have a scheduled follow-up within the assigned visit windows) without being lost to follow-up, the subject will be considered as having

missed the visit (which will be deemed to be a deviation from the CIP and the applicable form should be completed). If the subject has missed a visit, the subject shall return for subsequent follow-up visits.

A subject will be considered 'Lost to Follow-up' after two missed visits, a minimum of two unsuccessful phone calls from investigational site personnel to the subject or contact to schedule the next follow-up visit. These two phone calls must be documented in the subject's hospital records. If the subject is deemed lost to follow-up, a letter should be sent to the subject's last known address or to the subject's general practitioner (GP). A copy of the letter must be maintained in the subject's hospital records.

When subject withdrawal from the clinical investigation is due to an adverse event the subject will be followed outside of the clinical investigation until resolution of that adverse event or determination that the subject's condition is stable. The status of the subject's condition should be documented at the time of withdrawal.

In case of subject withdrawal, the site should make attempts to schedule the subject for a final study visit. At this final study visit, the subject will undergo the following assessments:

- Physical exam (PE)
- Evaluation and data collection of any reportable adverse events

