The adverse event is related to the study device/procedure – i.e. an event that follows a reasonable temporal sequence from administration of the study intervention, follows a known or expected response pattern to the suspected intervention, that is confirmed by improvement on stopping and reappearance of the event on repeated exposure and that could not be reasonably explained by the known characteristics of the subject's clinical state.

In summary, the **AE is related** to the study device (ADO II AS) or procedure if the event satisfies all of following criteria:

- Has a reasonable temporal relationship to intervention (e.g. device implant)
- Could not readily have been produced or explained by the subject's clinical state or have been due to environmental or other interventions
- Follows a known pattern of response to intervention
- Disappears or decreases with reduction in dose or cessation of intervention and recurs with re-exposure

Attempted ADO II AS Device Implant

Insertion of the TorqVue™ LP Catheter (9-TVLPC4F90/080) into the vasculature of the subject.

Major Complication

Major complications are defined as device (ADO II AS) or procedure-related adverse events resulting in any of the following:

- death,
- life-threatening adverse event,
- persistent or significant disability/incapacity, and/or
- a major open surgical intervention which is performed by a surgeon under general anesthesia

Examples of Major Complications:

- Device or procedure related events leading to death
- Cardiac perforation requiring percutaneous (e.g., pericardiocentesis) or open surgical intervention
- Cardiac tamponade
- Embolization requiring open surgical procedure (e.g., open heart surgery or femoral vessel cutdown procedure) to retrieve the device
- Persistent hemodynamic instability requiring emergency cardioversion/defibrillation therapy or emergency blood transfusion and/or institution of inotropic therapy
- Excessive blood loss or hemolysis requiring transfusion ≥ 20 cc/kg
- Persistent or worsening respiratory instability
- Cerebral or pulmonary embolism
- Persistent cardiac arrhythmia requiring a pacemaker
- Arteriovenous fistula requiring open surgical intervention
- False aneurysm of the femoral artery requiring surgical intervention
- Femoral vessel thrombophlebitis treated with intravenous antibiotics
- Infection of the device (bacterial endocarditis)

Minor Complication

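### Section 8.2 sets conflicting end points for following an already reported adverse event, so the course of an event still open when a subject leaves before day 180 may or may not reach the primary safety adjudication

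*Combined protocol and SAP*

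**What the plan says.** Section 8.2 (Adverse Event Reporting) speaks three times about when collection ends for a reported event.

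- First paragraph: safety surveillance and reporting run from enrolment until the last visit, death, the end of participation or withdrawal.
- Third paragraph: "Adverse events will be monitored until they are adequately resolved or the subject has ended his/her participation in the trial, whichever comes first".
- Later paragraph, after the list of reportable events: records of the subsequent course are to be kept and, as applicable, sent to the sponsor, with this end point: "until the event has subsided or, in case of permanent impairment, until the event stabilizes and the overall clinical outcome has been ascertained". It continues: "Adverse events will be monitored until they are adequately resolved. The status of the subject's condition should be documented at each visit". No participation limit appears here.

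Section 5.7 (Subject Withdrawal) has a narrower provision. For withdrawals caused by an adverse event it provides: "the subject will be followed outside of the clinical investigation until resolution of that adverse event or determination that the subject's condition is stable". It adds: "The status of the subject's condition should be documented at the time of withdrawal". It does not say that the later outcome is reported to the sponsor, and it is silent on open events in subjects who leave for other reasons.

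The primary safety endpoint (4.4.1, 6.1.1) is the rate of major complications through 180 days after an attempted implant. Appendix B defines an attempt as insertion of the delivery catheter. It defines a major complication as a device- or procedure-related event with one of four consequences: death, a life-threatening event, "persistent or significant disability/incapacity, and/or" major open surgery. Minor complications are those that do not meet that definition. Under section 5 and 5.3.3, subjects without a successful implant are followed to the 30-day visit and then withdrawn, and 5.3.3 refers their adverse event collection to 8.2.

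**The concern.** For an event that has been reported but is still open when the subject leaves, the first and third paragraphs of 8.2 tell the site it may stop, and the later paragraph tells it to carry on. Two sites can each comply with the section and still submit different histories of the same clinical course.

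This reaches the primary endpoint because part of the major/minor distinction depends on what the event leads to. An event that looks minor at exit may end in death, lasting disability or open surgery before day 180. Whether the CEC learns of that depends on which sentence the site followed. The issue is the outcome of events already reported before exit, not the detection of new events afterwards.

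**Working it through.** The point is textual. The plan states no figure for it, so there is nothing to reproduce; the arithmetic below only sets the scale.

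**Step 1. The rules applied to one case.** Take a subject who leaves before day 180 with a reported, related event still open.

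| Source | Reason for exit | Does collection continue after exit? |
|---|---|---|
| 8.2, first paragraph | any | No |
| 8.2, third paragraph | any | No |
| 8.2, later paragraph | any | Yes, to resolution or a known outcome |
| 5.7 | adverse event | Follow-up continues outside the investigation; reporting of the outcome is not stated |
| 5.7 | other | Not addressed |

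The rows for 8.2 give opposite answers. No visible text ranks them or limits either to a class of event.

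**Step 2. Who is exposed.** Only subjects who leave before day 180. One such group is planned: unsuccessful implants, which are attempts under Appendix B and so fall within the safety endpoint. Other early withdrawals are the second group. Subjects followed past day 180 are little affected.

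**Step 3. Length of the gap for the planned exits.** Table 5 puts the 1-month visit at 30 ± 7 days, that is day 23 to day 37.

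- Latest exit: 180 − 37 = 143 days; 143/180 = 79% of the window.
- Earliest exit: 180 − 23 = 157 days; 157/180 = 87% of the window.

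The early exit itself comes from section 5, not from 8.2. What 8.2 leaves undecided is whether an open event is followed across those days.

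**Step 4. Effect per event.** The sample-size section is redacted. Section 4.1 gives 40 as the number reaching 6 months before the PMA submission, so 40 as the safety denominator is an assumption. One event moved from minor to major changes the rate by 1/40 = 2.5 points. Subjects withdrawn at 30 days are not among those reaching 6 months. If they are added to the 40, the effect is slightly smaller: with two, 1/42 = 2.4 points; with four, 1/44 = 2.3 points.

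The exact binomial 95% intervals (the method named in 6.1.1.1) at n = 40 are:

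| Major complications | Rate | 95% interval |
|---|---|---|
| 0 | 0.0% | 0 to 8.8% |
| 1 | 2.5% | 0.1 to 13.2% |
| 2 | 5.0% | 0.6 to 16.9% |

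**Step 5. How many early exits.** No implant failure rate is given. For assumed rates f of 2%, 5% and 10% among 40 attempts, the expected number of planned exits is 40f = 0.8, 2 and 4. The chance of at least one is 1 − (1 − f)^40 = 55%, 87% and 98%. How many of those would have an open event cannot be derived from the documents.

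**The case against.** The strongest case against is that the conflict has no demonstrated effect on the endpoint. The later paragraph of 8.2 is phrased as an obligation, so a site that follows it supplies the outcome. Section 8.2.1 requires deaths to be reported once the site is aware, with no participation limit stated there. Section 5.9.2 gives adjudication to the CEC under a charter that is not in the documents, and text after the interval sentence in 6.1.1.1 is redacted. All of this stands as a limit on size. None of it tells a site which sentence of 8.2 governs.

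Four stronger readings are tempting but not supported:

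- A reader might infer that an event open at exit is automatically classed as minor. No passage sets such a default or confines the CEC to exit-day data.
- A reader might infer that any error must lower the safety rate. Several major criteria and examples in Appendix B turn on persistence, so an event judged persistent at exit could later resolve and be overcounted.
- A reader might infer that every classification depends on later outcome. Many listed majors are fixed when they occur or are treated, such as tamponade, embolization needing open surgery, or cerebral embolism.
- A reader might take 5.7 as a further conflicting rule. It is a specific provision for withdrawals due to an adverse event and partly covers that group. Its shortfall is that it does not say the outcome comes back to the study.

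**Conclusion.** The contradiction within 8.2 is real and can affect the 180-day primary safety rate, through one narrow route: a related event reported before exit, not major at exit, that becomes major after exit and by day 180. Undercounting is the main risk, because worsening that nobody collects cannot be counted; overcounting of events judged persistent at exit is possible.

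The number of such events is unknown, probably small and possibly zero. Each would move the rate by about 2.5 points if 40 attempted subjects are analysed, or slightly less if early exits enlarge the denominator. In a single-arm study whose safety result is a proportion with an exact interval, one event is visible: going from 0 to 1 in 40 raises the upper limit from 8.8% to 13.2%. This rests on the assumed denominator and on no handling rule existing in the redacted text or the CEC charter. Such a rule could reduce the consequence but would not remove the conflict in 8.2. The text should be reconciled; the documents do not show that the safety rate is biased.

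**What to change.** Reconcile the first, third and later paragraphs of 8.2, and align 5.7, into one data-collection rule that does not depend on the reason for exit. Editing only the third paragraph would leave the first still ending safety reporting at withdrawal. The rule could state that:

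- for any reported device- or procedure-related event open at exit, the outcome is collected by telephone or record review, consent permitting;
- collection runs until the event is resolved or stable, or at least through day 180 after the attempt, so that it covers the endpoint window;
- the outcome is sent to the CEC for final major or minor classification.

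The day-180 minimum goes beyond reconciling the existing text; it is proposed so that collection matches the endpoint. The change concerns data collection only, not treatment. The cost is a few edited sentences, some calls or record reviews for the few subjects who leave with an open event, and a safety rate that may come out less favourable.
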